4.3.2.3.1 Immediate Post-vaccination Surveillance Period

Subjects will be kept under observation for 30 minutes after vaccination to ensure their safety. The post-vaccination surveillance should be documented in the source document. Any AE that occurs during this period will be noted on the source document and recorded in the CRF, as follows:

- Any unsolicited systemic AE occurring during the first 30 minutes post-vaccination will be recorded on the CRF as immediate unsolicited systemic AE.
- Solicited and unsolicited injection site reactions and solicited systemic reactions will be recorded and analyzed as starting on the day of vaccination.

- Any SAE occurred during the first 30 minutes post-vaccination will be reported in the same way as any other SAE and to the Sponsor, according to the procedures described in the protocol.

4.3.2.3.2 Reactogenicity (Solicited Reactions From Day 0 to Day 07 After Vaccination)

After vaccination, subjects' parents / guardians will be provided with a safety diary card, a digital thermometer, and a flexible ruler, and will be instructed how to use them. The following items will be recorded by the subjects in the diary card on the day of vaccination and for the next 7 days (i.e., D0 to D07) until resolution:

- Daily temperature, with the route by which it was taken
- Daily measurement or intensity grade of all other solicited injection site and systemic reactions
- Action taken for each event, if any (e.g., medication)

The action taken by the parent or guardian to treat any solicited reactions will be classified in the CRF using the following scale:

- 0: None
- 1: Medication (self-medication with an existing prescription or over-the-counter medication)
- 2: Health care provider contact (no new medication prescribed)
- 3: Health care provider contact and prescription of a new medication (health care provider instructed subject to take a new medication, either an over-the-counter medication or one requiring a written prescription)
- 4: Hospitalization (inpatient)

Subjects' parents / guardians will be contacted by telephone 8 days after vaccination to remind them to record all safety information in the diary card.

If the timing of the telephone call should fall on a weekend or a holiday, the call should be made on the next business day. If contact is not made on the designated day, study staff will continue calling until contact is made. Every telephone attempt and its outcome will be documented in the source document.

[Table 4.1](#) and [Table 4.2](#) present, respectively, the injection site reactions and systemic reactions that are prelisted in the diary cards and CRF, together with the intensity scales.

Table 4.1: Solicited injection site reactions: terminology, definitions, and intensity scales

CRF term (MedDRA lowest level term [LLT])	Injection site pain*	Injection site erythema	Injection site swelling
Diary card term	Pain	Redness	Swelling
Definition		Presence of a redness including the approximate point of needle entry	Swelling at or near the injection site Swelling or edema is caused by a fluid infiltration in tissue or cavity and, depending on the space available for the fluid to disperse, swelling may be either soft (typically) or firm (less typical) to touch and thus can be best described by looking at the size of the swelling
Intensity scale*	Grade 1: Easily tolerated Grade 2: Sufficiently discomforting to interfere with normal behavior or activities Grade 3: Incapacitating, unable to perform usual activities	Grade 1: > 0 to < 25 mm Grade 2: ≥ 25 to < 50 mm Grade 3: ≥ 50 mm	Grade 1: > 0 to < 25 mm Grade 2: ≥ 25 to < 50 mm Grade 3: ≥ 50 mm

*For the subjective reaction of pain, subjects or parents / guardians will record the intensity level (Grade 1, 2, or 3) in the diary card. For the measurable reactions of redness and swelling, they will record just the size of the reaction, and the classification as Grade 1, 2, or 3 will be assigned at the time of the statistical analysis.

Table 4.2: Solicited systemic reactions: terminology, definitions, and intensity scales

CRF term (MedDRA LLT)	Fever	Headache	Malaise	Myalgia
Diary card term	Temperature	Headache	Feeling unwell	Muscle aches and pains
Definition	Elevation of temperature to $\geq 100.4^{\circ}\text{F}$ ($\geq 38.0^{\circ}\text{C}$)	Pain or discomfort in the head or scalp. Does not include migraine.	General ill feeling. Malaise is a generalized feeling of discomfort, illness, or lack of well-being that can be associated with a disease state. It can be accompanied by a sensation of exhaustion or inadequate energy to accomplish usual activities.	Muscle aches and pains are common and can involve more than one muscle at the same time. Muscle pain can also involve the soft tissues that surround muscles. These structures, which are often referred to as connective tissues, include ligaments, tendons, and fascia (thick bands of tendons). Does not apply to muscle pain at the injection site which should be reported as injection site pain.
Intensity scale*	Grade 1: $\geq 100.4^{\circ}\text{F}$ to $\leq 101.1^{\circ}\text{F}$ or $\geq 38.0^{\circ}\text{C}$ to $\leq 38.4^{\circ}\text{C}$ Grade 2: $\geq 101.2^{\circ}\text{F}$ to $\leq 102.0^{\circ}\text{F}$ or $\geq 38.5^{\circ}\text{C}$ to $\leq 38.9^{\circ}\text{C}$ Grade 3: $\geq 102.1^{\circ}\text{F}$ or $\geq 39.0^{\circ}\text{C}$	Grade 1: No interference with activity Grade 2: Some interference with activity Grade 3: Significant; prevents daily activity	Grade 1: No interference with activity Grade 2: Some interference with activity Grade 3: Significant; prevents daily activity	Grade 1: No interference with activity Grade 2: Some interference with activity Grade 3: Significant; prevents daily activity

*For all reactions but fever, subjects or parents / guardians will record the intensity level (Grade 1, 2, or 3) in the diary card. For fever, they will record the body temperature, and the classification as Grade 1, 2, or 3 will be assigned at the time of the statistical analysis.

Important notes for the accurate assessment of temperature:

Parents / guardians are to measure body temperature once per day, preferably always at the same time. The optimal time for measurement is the evening, when body temperature is the highest. Temperature is also to be measured at the time of any apparent fever. The observed daily temperature and the route of measurement are to be recorded in the diary card, and the highest temperature will be recorded by the site in the CRF. The preferred route for this trial is axillary. Pre-vaccination temperature is also systematically collected by the investigator on the source document. Tympanic thermometers must not be used.

4.3.2.3 Unsolicited Non-serious Adverse Events From Day 0 to Day 30 After Vaccination

In addition to recording solicited reactions, parents / guardians will be instructed to record any other medical events that may occur during the 30-day period after vaccination. Space will be provided in the diary card for this purpose.

For each unsolicited non-serious AE, the following information is to be recorded:

- Start and stop dates^a
- Intensity of the event:
 - For measurable unsolicited non-serious AEs that are part of the list of solicited reactions, the size of the AE as well as the temperature for fever will be collected and analyzed based on the corresponding scale used for solicited reactions (see [Table 4.1](#) and [Table 4.2](#))
 - Other unsolicited non-serious AEs will be classified according to the following intensity scale:
 - Grade 1: No interference with activity
 - Grade 2: Some interference with activity
 - Grade 3: Significant; prevents daily activity
- Action taken for each AE, if any (e.g., medication)

The action taken by the parent or guardian to treat any unsolicited AEs will be classified in the CRF using the following scale:

- 0: None
- 1: Medication (self-medication with an existing prescription or over-the-counter medication)
- 2: Health care provider contact (no new medication prescribed)

^a The stop date of all related AEs will be actively solicited. For other events, the investigator will provide the stop date when it becomes available. AEs for which no stop date was obtained during the course of the trial will be considered as ongoing at the end of the trial.

unsolicited AEs collected for this post-vaccination period. MAAEs that occur from Visit 2 (D30 [+14 days]) to D180 (+14 days) will be recorded as such in the memory aid. An MAAE that occurs within the study period but meets the definition of an SAE should be reported only on the SAE Reporting Form, but not on the MAAE page of the CRF. The Investigator will assess the causal relationship between the MAAE and the investigational or study product as either “Not related” or “Related”, as described in [Section 4.3.2.3.7](#).

4.3.2.3.7 Assessment of Causality

The Investigator will assess the *causal relationship* between each unsolicited systemic AE and vaccination as either not related or related, based on the following definitions^a:

- 0: Not related – The AE is clearly / most probably caused by other etiologies such as subject’s underlying condition, therapeutic intervention, or concomitant therapy; or the delay between vaccination and the onset of the AE is incompatible with a causal relationship; or the AE started before the vaccination (screening phase, if applicable)
- 1: Related – There is a “reasonable possibility” that the AE was caused by the vaccination, meaning that there is evidence or arguments to suggest a causal relationship

Note: By convention, all injection site AEs (solicited and unsolicited) and all solicited systemic reactions are considered to be related to vaccination and referred to as reactions, and therefore do not require the Investigator’s opinion on relatedness.

AEs likely to be related to the product, whether serious or not, that persist at the end of the trial will be followed up by the Investigator until their complete disappearance or the stabilization of the subject’s condition. The Investigator will inform the Sponsor of the date of final disappearance of the event.

4.4 Derived Endpoints: Calculation Methods

4.4.1 Safety

4.4.1.1 Solicited Reactions

4.4.1.1.1 Daily Intensity

All daily records for solicited reactions will be derived into daily intensity according to the following classification: None, Grade 1, Grade 2, Grade 3, or Missing.

For the derivation of daily intensities the following sequential steps will be applied:

- 1) Solicited reactions (except Fever) with an investigator presence recorded as “No” and with all daily records missing then all daily intensities will be derived as None.

^a ICH Guidelines, Clinical Safety Data Management E2A

- 2) For a temperature partially missing after decimal point, the data will be analyzed replacing “MD” (missing data) by zero. For example, a “39.MD” daily temperature will be considered as “39.0°C” at the time of analysis.
- 3) For non-measurable solicited reactions, daily intensities will correspond to daily records reported in the clinical database. For measurable solicited reactions the daily measurements reported in the clinical database will be converted based upon the intensity scales defined in the protocol; this assumes a reaction that is too large to measure (non-measurable, “NM”) is Grade 3.

Note: The maximum intensity on the ongoing period is derived from the record of the maximum intensity/measurement after the end of the solicited period following the rule described above.

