4.4.1.1.2 Maximum Overall Intensity

Maximum overall intensity is derived from the daily intensities computed as described in [Section 4.4.1.1.1](#) and is calculated as the maximum of the daily intensities over the period considered.

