4.4.1.1.3 Presence

Presence is derived from the maximum overall intensity on the period considered:

- None: No presence
- Grade 1, Grade 2, or Grade 3: Presence
- Missing: Missing presence

Subjects with at least one non-missing presence for a specific endpoint will be included in the analysis. Conversely, those without a non-missing presence will not be included in the analysis of the endpoint.

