4.4.1.1.4 Time of Onset

Time of onset is derived from the daily intensities computed as described in [Section 4.4.1.1.1](#). It corresponds to the first day with intensity of Grade 1, Grade 2, or Grade 3.

Note: If a reaction is not continuous (i.e., reaction occurs over two separate periods of time intervened by at least one daily intensity Missing or None) then the time of onset is the first day of the first occurrence.

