4.4.1.1.5 Number of Days of Occurrence

Number of days of occurrence over the period considered is derived from the daily intensities computed as described in [Section 4.4.1.1.1](#). It corresponds to the number of days with daily intensities of Grade 1, Grade 2, or Grade 3. Number of days of occurrence on the solicited period with a specified intensity may also be derived.

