4.4.1.1.7 Ongoing

Ongoing is derived from the last daily intensity of the solicited period computed as described in [Section 4.4.1.1.1](#) and the maximum intensity on the ongoing period. The investigator's ongoing flag is not used because the measurement would determine the ongoing status of the reaction.

If the last daily intensity of the solicited period is at least Grade 1 and maximum intensity on the ongoing period is also at least Grade 1, then the reaction is considered ongoing. In any other cases the reaction will not be considered as ongoing.

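### For non-fever solicited reactions with no daily records, an investigator No is kept as a non-event but a Yes is dropped, so any such Yes left after data review lowers the reported percentage slightly

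*SAP*

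**What the plan says.** SAP 4.4.1.1.1 derives the daily intensity of solicited reactions in sequential steps. Step 1 is the only one that uses the investigator's presence answer: "Solicited reactions (except Fever) with an investigator presence recorded as “No” and with all daily records missing then all daily intensities will be derived"; the value it assigns is None. Fever is outside this step.

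Step 3 covers what remains. For reactions graded by the parent, "daily intensities will correspond to daily records reported in the clinical database". For redness and swelling, intensity comes from the recorded daily measurements.

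The later derivations build on these daily values:

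- 4.4.1.1.2: the maximum overall intensity "is calculated as the maximum of the daily intensities over the period considered".
- 4.4.1.1.3: presence follows from that maximum, with "Missing: Missing presence", and "those without a non-missing presence will not be included in the analysis of the endpoint".
- 4.4.1.1.4, time of onset: "It corresponds to the first day with intensity of Grade 1, Grade 2, or Grade 3".
- 4.4.1.1.5, number of days: "It corresponds to the number of days with daily intensities of Grade 1, Grade 2, or Grade 3".

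Section 5.3.1.4 sends missing solicited intensities back to 4.4.1.1.1, and 5.3.1 rules out replacement of missing safety data. Section 5.6 announces a data review before lock but gives no rule for this case.

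**The concern.** Two subjects can have the same gap in the diary data and differ only in the investigator's answer. The one with a No is analysed as a subject without the reaction. The one with a Yes is removed from numerator and denominator alike. Known non-reactors are kept and known reactors are lost, so the error can go only one way.

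The SAP treats a comparable case differently. Under 4.4.1.2.1 and 5.3.1.4, an unsolicited non-serious AE with a verbatim term is counted even when its intensity is missing. A solicited reaction that the investigator has affirmed, also of unknown grade, is not.

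At stake are the reported percentages of subjects with pain, redness, swelling, headache, malaise or myalgia. There is also a side effect in 4.4.1.5.5. The table by system organ class and preferred term (SOC/PT) accepts only events of at least Grade 1, so an ungraded reaction flagged as leading to termination would not appear there.

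**Working it through.** **Following the rules, non-fever reaction, all daily records missing**

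| Step | Investigator No | Investigator Yes |
|---|---|---|
| Daily intensity (4.4.1.1.1) | None, by step 1 | Missing, by step 3 |
| Maximum (4.4.1.1.2) | None | Missing |
| Presence (4.4.1.1.3) | No presence | Missing |
| In the analysis? | Yes, as a non-event | No |

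Nothing in 5.3.1 or 5.3.1.4 changes the right-hand column.

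**Size**

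The SAP states no figure on this point, so there is none to reproduce. The inputs are:

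- n = 500 per group (3.1), with Clopper-Pearson 95% CIs (5.1.3.2.2).
- Assumed: p, the true reaction rate; m, the share of subjects with no daily records; a, the share of those with an investigator answer. Both m and a are taken as unrelated to reaction status.

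Under the present rule, the numerator is the reactors with records. The denominator is all subjects with records plus the No answers without records:

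r = (1 - m)p / [(1 - m) + m·a·(1 - p)]

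With a = 100%:

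| m | p = 40% | Bias (points) | p = 10% | Bias (points) |
|---|---|---|---|---|
| 1% | 0.396/0.996 = 39.8% | -0.24 | 0.099/0.999 = 9.91% | -0.09 |
| 2% | 0.392/0.992 = 39.5% | -0.48 | 0.098/0.998 = 9.82% | -0.18 |
| 5% | 0.380/0.980 = 38.8% | -1.22 | 0.095/0.995 = 9.55% | -0.45 |

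With a = 50% and m = 5%, the results are 0.380/0.965 = 39.4% (-0.62) and 0.095/0.9725 = 9.77% (-0.23). With m = 0 or a = 0 there is no bias.

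In counts, for p = 40%, m = 5%, a = 100%: 25 of 500 subjects lack records, 15 with No and 10 with Yes. The present rule gives 190/(475 + 15) = 190/490 = 38.8% (95% CI 34.4 to 43.3). Using both answers gives 200/500 = 40.0% (35.7 to 44.4).

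**Against sampling error.** The Clopper-Pearson interval is 35.68% to 44.44% for 200/500 (half-width 4.38 points) and 7.51% to 12.97% for 50/500 (half-width 2.73 points). Every bias in the table is smaller.

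**Between groups.** Equal p and equal m give no spurious difference. With m = 5% in both groups, a true 40% against 30% is reported as 38.78% - 28.93% = 9.8 points instead of 10 (28.93% = 0.285/0.985). If m were 2% in one group and 5% in the other at p = 40%, a spurious difference of 39.52% - 38.78% = 0.74 point would arise.

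**Effect of a correction on the grade rows.** Assume a true Grade 3 rate of 5%, with p = 40%, m = 5%, a = 100%. The present rule gives 0.05 × 0.95 / 0.98 = 4.85%. Putting the ungraded Yes subjects in that denominator as well gives 0.0475 / 1 = 4.75%, further from 5%. Using only subjects of known intensity, None included, leaves it at 4.85%.

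**The case against.** The strongest objection is that the case may never arise. The SAP does not show the CRF or its edit checks. It calls assessment of solicited reactions mandatory (4.3.2.1). The diary is reviewed with the parent at Visit 2 (3.2), the investigator asks about solicited reactions there (4.3.2.3), and data are reviewed before lock (5.6). A Yes with no grade on any day may not survive all that. This stands: the frequency is unknown and may be zero.

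Related to this, the form may let No be entered without daily fields. A No with blank days would then be the ordinary record of a non-reactor, and a Yes with blank days a rare data error. This also stands as a limit on the size, but it does not remove the bias. With a = 100% the formula reduces to p(1 - m)/(1 - mp). There only the share of reactors with a Yes and no records matters, and the number of No subjects without records drops out.

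A third argument is that No settles every day as None while Yes settles neither day nor grade. That explains the daily rule. It does not explain why the subject leaves the count of any reaction, for which a grade is not needed.

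Section 4.4.1.1.7 might be cited as policy, since the investigator's "ongoing flag is not used because the measurement would determine the ongoing status of the reaction". That sentence concerns ongoing status, and step 1 itself relies on the investigator's answer.

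A reader might also infer that such a reaction vanishes from all reporting of discontinuations. The text does not support that. Under 4.4.1.5.5 the disposition table counts from the reason on the termination form. The safety overview accepts that reason as one of two alternatives, and the Grade 1 condition reads most naturally as attached to the other. Only the SOC/PT table is affected.

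**Conclusion.** The asymmetry is real and follows from the rules as written. The outcome for a Yes is determinate, and the direction of the bias is fixed: any such case left after data review lowers the reported percentage of subjects with that reaction.

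Its size is not known from the document. The figures of -0.2 to -1.2 points at 40% and -0.1 to -0.45 points at 10% rest on assumed shares of 1% to 5% without daily records, an answer available for all of them, and absence of records unrelated to reaction status.

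A reader might infer that the safety tables are materially biased or that the vaccine comparison is distorted. The SAP supports neither. It does not show that such cases occur, and the bias over this range stays below sampling error. The rule is the same in both groups, safety is descriptive with no hypothesis, and the primary non-inferiority test does not use these data. This is a minor correction, worth making because it is cheap.

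**What to change.** Keep step 1 of 4.4.1.1.1 and add one exception to the mapping in 4.4.1.1.3. For non-fever solicited reactions with investigator presence Yes and all daily records missing, set presence to Yes and maximum intensity to Missing. Then:

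- Count the subject in the numerator and denominator of the row for any reaction only. Under the assumptions above this recovers p for any a: [(1 - m)p + m·a·p] / [(1 - m) + m·a] = p.
- Show the number with missing intensity per group, even if it is zero.
- Compute the Grade 1, 2 and 3 rows among subjects with known intensity, None included, so that they are not diluted.
- Set time of onset (4.4.1.1.4) and the number of days (4.4.1.1.5 and 4.4.1.1.6) to Missing. Read literally, the present count of graded days would return zero for a subject counted as having the reaction.
- In 4.4.1.5.5, state that the Grade 1 condition does not remove such a reaction from the SOC/PT table when it is flagged as leading to termination.

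The cost is a few sentences and derivation lines, one extra row in the solicited-reaction tables, and slightly different denominators for the any row and the grade rows when such cases exist. The grade rows stay where the present rule puts them. They are not corrected, because the grades are not known.

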4.4.1.1.2 Maximum Overall Intensity

Maximum overall intensity is derived from the daily intensities computed as described in [Section 4.4.1.1.1](#) and is calculated as the maximum of the daily intensities over the period considered.

4.4.1.1.3 Presence

Presence is derived from the maximum overall intensity on the period considered:

- None: No presence
- Grade 1, Grade 2, or Grade 3: Presence
- Missing: Missing presence

Subjects with at least one non-missing presence for a specific endpoint will be included in the analysis. Conversely, those without a non-missing presence will not be included in the analysis of the endpoint.

4.4.1.1.4 Time of Onset

Time of onset is derived from the daily intensities computed as described in [Section 4.4.1.1.1](#). It corresponds to the first day with intensity of Grade 1, Grade 2, or Grade 3.

Note: If a reaction is not continuous (i.e., reaction occurs over two separate periods of time intervened by at least one daily intensity Missing or None) then the time of onset is the first day of the first occurrence.

